available data for laser ablation, this analysis provides the best current estimate for a success or performance threshold of laser ablation to match the well-documented long-term effectiveness of ATL. Therefore, this study compares safety and efficacy outcomes of laser ablation to the threshold determined by Attiah et al.³⁰

Seizure control is expected to yield improvements in health-related quality of life. Primary and secondary endpoints of this study have been designed to evaluate these outcomes. Additional secondary endpoints have been designed to further evaluate the cognitive outcomes after the Visualase procedure.

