7.17 Retreatment

Subjects who fail to achieve Engel Class I seizure freedom or whose procedure could not be completed as intended prior to discharge may be evaluated for retreatment. Retreatment is defined as a subsequent Visualase procedure after the subject's discharge following the initial Visualase procedure, to treat MTLE ipsilateral to the initial Visualase procedure and also within the temporal lobe. If it is determined that the ablation of additional tissue within the original target site may improve the outcome, the

justification for retreatment and supporting evidence will be entered on an eCRF and submitted to the Pre-Surgical Evaluation Committee for assessment per Section 7.12. Justification and supporting evidence for consideration of retreatment may include, but is not limited to, EEG demonstrating interictal and ictal discharges from the same temporal lobe, MRI showing no other lesions, same type of seizure behavior and auras, and no evidence of extra-temporal lesions.

If the Pre-Surgical Evaluation Committee disagrees with the recommendation for retreatment, the subject may continue participation in the study per their original follow-up schedule without retreatment. Alternatively, the subject may be withdrawn from the study.

If the committee agrees with the recommendation for retreatment, the subject may be scheduled for an additional Visualase procedure. Retreated subjects will have the same assessments at the same intervals as they would for an initial procedure. The new follow-up visit windows will be calculated based on the date of the retreatment Visualase procedure.

Subjects retreated with Visualase after the subject's discharge from the original Visualase procedure will be considered to have failed the primary efficacy endpoint. However, their data will contribute to specified secondary endpoints.

Subjects who undergo open resection after a Visualase procedure will be considered to have failed the primary efficacy endpoint. Seizure and AE data will be collected per the standard of care for the site.

Subjects who are retreated with Visualase or undergo open resection after a Visualase procedure will be followed for 12 months after the secondary procedure, or until the last enrolled subject completes Follow-up Visit 4 (12 months), whichever occurs first.

All subjects will be assessed for safety for the duration of their participation in this study, regardless of whether they are retreated.

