7.4 Handling of Missing, Unused, and Spurious Data and Dropouts

7.4.1 Missing Data

Missing primary efficacy endpoint values and missing secondary endpoint values associated with testable hypotheses will be imputed for analysis with the mITT analysis population. Missing primary efficacy endpoint data will be imputed as a binary outcome of seizure freedom, regardless of missing pattern. No daily level imputation will be conducted.

The primary method of imputation will be multiple imputation (SAS PROC MI followed by MIANALIZE). Ten repetitions will be performed and, if needed, will be increased until the algorithm converges.

The Markov chain Monte Carlo (MCMC) method or Fully Conditional Specification (FCS) will be used with the default number of burn-in iterations before the imputation. The model variables will include: age, sex, race (white, African American, or other), and duration of disease.

SLATE Statistical Analysis Plan		Form
Revision 1.0	Page 10 of 23	Medtronic

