7.9.3.5 Secondary Endpoint #5

Within-subject change of the Quality of Life in Epilepsy inventory (QOLIE-31) score (English language version), from baseline to 12 months following the Visualase procedure, categorized as -1 if the decrease is clinically significant (\leq -11.8), categorized as 0 if not clinically significant (-11.7 to +11.7), and categorized as +1 if the increase is clinically significant (\geq 11.8).

It is hypothesized that the QOLIE-31 score will increase (improve) from baseline to 12 months following the Visualase procedure. The hypotheses associated with this endpoint are as follows:

Null Hypothesis: M (V-QOLIE-31 - BSL-QOLIE-31) \leq 0 Alternate Hypothesis: M (V-QOLIE-31 - BSL-QOLIE-31) > 0

Where M (V-QOLIE-31 - BSL-QOLIE-31) = sign-test statistic ([increases-decreases]/2) in the Quality of Life in Epilepsy inventory from baseline to Month 12 post Visualase.

A sign test will be used to determine if the median categorical change is significantly greater than zero. The Minimally Clinically Important Difference (MCID) of 11.8 points for the QOLIE-31 is based on published literature (Wiebe 2002).

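### The listed imputation variables for secondary endpoints 3–7 cannot tell treatment failures from seizure-free subjects, although missing 12-month scores are likely to concentrate among failures

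*Protocol*

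**What the plan says.** Endpoints 3–7 (Protocol 14.6.3–14.6.7, SAP 7.9.3.3–7.9.3.7) are changes from baseline to Month 12 in the Boston Naming Test, the RAVLT 5-trial total, QOLIE-31 and the two SF-36 component scores. All use the English-language subset. For QOLIE-31, for example: "It is hypothesized that the QOLIE-31 score will increase (improve) from baseline to 12 months following the Visualase procedure".

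Protocol 7.17 describes two routes after the first ablation.

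- **Retreatment.** "Retreated subjects will have the same assessments at the same intervals as they would for an initial procedure", and "The new follow-up visit windows will be calculated based on the date of the retreatment Visualase procedure". Follow-up lasts 12 months after the secondary procedure "or until the last enrolled subject completes Follow-up Visit 4 (12 months), whichever occurs first". On use of the results: "However, their data will contribute to specified secondary endpoints".
- **Open resection.** "Seizure and AE data will be collected per the standard of care for the site". Cognitive and QOL testing is not mentioned.

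Both groups count as failures on the primary efficacy endpoint. In the visible text only secondary endpoint 2 has a rule for retreated subjects (Protocol 14.6.2, SAP 7.9.3.2).

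SAP 7.4.1 multiply imputes missing values of tested secondary endpoints in the mITT set: "The model variables will include: age, sex, race (white, African American, or other), and duration of disease".

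**The concern.** Imputation from a set of covariates is sound if, given those covariates, subjects with missing scores resemble those with observed scores. Here the plan itself gives reasons for scores to be missing that are tied to failure: resection without a stated test battery, and a restarted follow-up that study closure can truncate. Age, sex, race and disease duration carry no information on whether the ablation worked. The model would fill in such subjects from a pool that the sample-size section expects to be mostly seizure free.

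The protocol expects outcome and QOL to move together: "Seizure control is expected to yield improvements in health-related quality of life". A failure given a pool-average QOL change is therefore likely to look better than it should. Endpoints 5–7 are tested hypotheses in an alpha-controlled sequence, so this could affect a confirmatory claim. The same subject would be a failure on the primary endpoint and, on average, an ordinary improver on QOL.

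**Working it through.** **1. The plan's own figures.** With n = 150, the exact two-sided 95% lower bound first exceeds 43% at 77 successes (bound 0.4305; at 76 it is 0.4239). P(X ≥ 77 | n = 150, p = 0.56) = 0.891, which reproduces the stated 89%. Also 150/0.70 = 214.3, so 215; 150 × 0.73 = 109.5, stated as 109; 109 × 0.5 = 54.5, stated as 55. The 86% power for the neuropsychological tests at N = 55 cannot be checked, because its effect size is not given.

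**2. What is known and what is modelled.**

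| Item | Collected? | Listed in SAP 7.4.1? |
|---|---|---|
| Age, sex, race, disease duration | yes | yes |
| Same instrument at baseline | yes (Table 2) | no |
| Same instrument at 6 months | yes (Table 2; RAVLT uses Form GE-AB, not Form A) | no |
| Engel I status at 12 months | yes; failure is fixed by rule for crossovers (7.17) | no |
| Retreatment or resection | yes (Secondary Procedure form, Table 4) | no |

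**3. Illustration for QOLIE-31.** Let m be the share of the English subset who are failures with an imputed score. The documents give neither m nor any QOL response rate, so all of the following are assumptions except the 56%:

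- m = 5% to 15%;
- improved/worsened 55%/5% if seizure free and 25%/15% if not;
- own outcome of an imputed failure, without the benefit of a second procedure, between 25%/15% (net +0.10) and 15%/20% (net −0.05).

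The share seizure free among the rest is s = 0.56/(1 − m). The imputed net is s(0.55 − 0.05) + (1 − s)(0.25 − 0.15) = 0.10 + 0.40s. The bias is m × (imputed net − own net).

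- m = 5%: s = 0.589, imputed net 0.336, gap 0.236 to 0.386, bias 1.2 to 1.9 percentage points.
- m = 10%: s = 0.622, imputed net 0.349, gap 0.249 to 0.399, bias 2.5 to 4.0 points.
- m = 15%: s = 0.659, imputed net 0.364, gap 0.264 to 0.414, bias 4.0 to 6.2 points.

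**4. Effect on the sign test** (two-sided 0.05, imputation variance ignored).

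- Rates as in step 3: at N = 55, power is 94–97% with failures filled in as average and 88–92% with their own outcomes. At N = 109 it is at least 99.6% either way.
- Weaker assumed effects (35%/15% in the pool, 10%/30% in imputed failures), N = 109: net 0.20 and power 83% when filled in as average. With their own outcomes at m = 10%, net = 0.9 × 0.20 + 0.1 × (−0.20) = 0.16 and power is 63%.

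The consequence thus runs from negligible to substantial, depending on figures that the documents do not give.

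**5. What Engel status would recover.** With it in the model, an imputed failure draws from other non-seizure-free subjects, net +0.10 in step 3. The gap falls from 0.24–0.41 to 0–0.15 per imputed subject, or at most 0.15 × 15% = 2.25 points overall.

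**6. Endpoints 3–4.** The mean shifts by m × (difference in change). For m = 5–20% and an assumed difference of 5–15 points, that is 0.25 to 3.0 points on the Boston Naming Test, against a 5-point margin. The sign is not settled: it depends on whether the effect of a resection or second ablation on cognition is meant to count.

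**The case against.** A reader might infer that crossover subjects have no usable 12-month score, or that the plan chooses to credit them with a second ablation. The documents do not support either. Retreated subjects have a full battery planned 12 months after the last ablation unless closure cuts it off. Those who cross over after Visit 3 have 6-month scores, and after Visit 4 the 12-month score is already taken. Nothing in Protocol 7.15 cancels Visit 4 after resection; 7.17 is silent on cognitive and QOL tests rather than excluding them. The endpoints to which retreated subjects contribute are left undefined for 3–7, which is an open rule and not a stated practice.

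Nor does a bias towards the device follow for endpoints 3–4. A second ablation could lower naming or memory scores and count against non-inferiority. Whether the cognitive effect of resection belongs in the estimate is a choice of estimand.

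Four further points have weight.

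- The range in step 3 applies only to failures whose score is actually imputed. Reading m as the whole crossover share overstates it.
- Retreatment is also open to subjects whose procedure could not be completed, so not every crossover is a failed complete ablation.
- If the target were QOL at 12 months whatever followed, a successful resection could raise the true score and weaken the claimed direction for endpoints 5–7.
- The visible SAP numbering goes from 7.4.1 to 7.4.3, Protocol 14.3.3 and 14.3.4 are not visible, and the variable list is not expressly exhaustive. A rule may exist in text that was withheld.

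These narrow the point. They do not make the four listed variables informative about treatment failure.

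**Conclusion.** The point holds as a weakness of the imputation model as listed. Missing 12-month scores are likely to concentrate in failures, and better predictors already collected are not listed. For endpoints 5–7 the imputed changes would tend to be too favourable. This rests on QOL following seizure control, as the protocol expects, and on the target being the effect of the ablation without credit for a later operation. For endpoints 3–4 the direction is uncertain.

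The size is undetermined. The 1.2 to 6.2 points are an illustration on assumed rates, not an estimate for this trial. Endpoints 3–7 are reached only if the primary endpoint and secondary endpoints 1 and 2 succeed, so the primary claim is untouched. The change is worth making because it improves on the stated method at almost no cost. The missing Month 12 anchor is a lesser matter of specification to settle at the same time.

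**What to change.** 1. **SAP 7.4.1.** For endpoints 3–7, add the same instrument's baseline score, its 6-month score where available, and 12-month Engel I status or crossover status. Engel I status is the safer default: a crossover term cannot be estimated if few crossovers have scores. Enter subjects whom Protocol 7.17 already counts as primary failures as not Engel I. Note the different RAVLT form at 6 months, so that score serves as a predictor and not as a substitute for the 12-month value.
2. **SAP 7.9.3.3–7.9.3.7.** State which Visualase procedure anchors Month 12 for retreated subjects, and how a score taken after open resection is handled. Which handling is primary is for the sponsor to choose and justify.
3. **Sensitivity analysis.** Report endpoints 3–7 under the alternative handling, with the number of retreated and resected subjects and how many of their scores were observed or imputed.

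Cost: SAP wording and minor programming before database lock. The added variables are already collected, and no visits are needed. The QOL results may become slightly less favourable.

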7.18 Healthcare Services Utilization

To assess use of healthcare resources specifically associated with epilepsy and the Visualase procedure, healthcare services utilization information will be collected during the Visualase procedure and hospital stay, and for any AEs requiring healthcare resources. Healthcare services utilization related to epilepsy and/or the Visualase procedure includes length of hospital stay, length of stay in ICU, ER visits, AEDs and psychotropic medications, physician office visits, and hospital readmissions.

7.19 Study Exit

A study exit eCRF is required for all subjects. Prior to exiting a subject from the study, it is recommended to follow the subject until all ongoing device-related, anesthesia-related, and/or procedure-related AEs are resolved or unresolved with no further actions planned. Upon exiting from the study, no further study data will be collected and no further study visits will occur for the subject. All data available through the time of the subject's exit will be used for analysis.

Subjects are urged to remain in the study as long as possible but may be exited from the study for any of the following situations:

- Subject has completed follow-up
- Subject lost to follow-up

- Subject death
- Subject did not meet inclusion/exclusion criteria (If ineligibility is discovered after the Visualase procedure, the subject will still be followed through 12 months post procedure.)
- Subject chooses to withdraw (e.g., consent withdrawal, relocation to another geographic location)
- Investigator deems withdrawal necessary (e.g., the subject enrolls in a confounding investigational study, the subject fails to maintain adequate study compliance, or it is medically necessary or in the best interest of the subject)

The following information is required to be documented at study exit:

- Reason for exit
- Date of study exit
- If the subject is determined to be lost to follow-up, details of a minimum of 3 contact attempts via 2 different methods (e.g., email, phone, and/or certified letter) must be recorded.

7.20 Medications

All prescription medications for an epilepsy or psychiatric indication (including rescue medications as taken) will be recorded on an electronic medication log from the time of enrollment. Generic medication names and doses will be captured, and any changes will be recorded on the medication log.

AEDs and their doses should remain stable from 30 days prior to the procedure through the final visit. Transient weans of AEDs prior to the Visualase procedure are permitted for patient safety, and intravenous doses of AEDs during the procedure are permitted.

Therapy considered necessary for the subject's welfare may be given at the discretion of the Investigator.

AED changes will be evaluated per Section 14.3.4.

7.21 Role of the Sponsor Representatives

Sponsor representatives may provide support as required for the study, including:

- Study training relevant to the involvement of personnel conducting study activities and Investigator responsibilities
- Technical support during the Visualase procedure under the supervision of a study Investigator
- Intraoperative data collection support (e.g., acquisition of system logs and files from the Visualase workstation) under the supervision of a study Investigator, but no data entry will be performed by Medtronic personnel or their representatives at sites
- Monitoring and auditing activities

8 INVESTIGATIONAL DEVICE / EQUIPMENT STORAGE, HANDLING AND TRACEABILITY

The Visualase System comprises a laser energy source, a pump for circulating coolant through the applicator, a computer workstation (Visualase capital equipment), and a

cooled laser applicator system and optional neuro accessory kit (Visualase disposables). All components of the Visualase System are FDA-cleared for use in neurosurgical procedures.

As the Visualase System is commercially released, no special receipt, storage, or reconciliation requirements apply. Management of Visualase System inventories by investigational sites will be in accordance with their respective operating policies.

Visualase capital equipment and disposables will enter the accountability system when they are accessed/opened with the intent to be used within the context of the study, at which point they become "investigational devices." Therefore, none of the Visualase capital equipment and disposables will be labelled as investigational, and the date they are accessed/opened with the intent to be used within the context of the study will be considered the date of receipt by the site.

For each Visualase disposable opened with the intent of being used within the context of the study, the following information will be documented:

- Model Number
- Lot number
- Date used/opened
- Subject ID
- Date returned/disposed
- Final disposition
- Reason for return/method of disposal
- Name/initials of the person who returned or disposed the device
- Quantity

For Visualase capital equipment, the following information will be documented:

- Model number
- Serial number
- Date installed
- Date returned/disposed (if applicable)
- Final disposition
- Reason for return/method of disposal
- Name/initials of the person who returned or disposed the device (if applicable)
- Quantity

Additionally, use and disposition of investigational devices will be documented and tracked on eCRFs.

The Sponsor will cover the cost of investigational disposables for study procedures.

9 STUDY DEVIATIONS

The investigator should not deviate from the CIP, except under emergency circumstances to protect the rights, safety or well-being of human subjects. A study deviation is defined as an event within a study that did not occur according to the CIP or the Clinical Trial Agreement, including, but not limited to, the following:

- Failure to obtain informed consent prior to participation in the study
- Incorrect version of the consent form rendered to the subject
- Failure to obtain IRB approval before conducting study-related activities

- Enrollment of subjects during lapse of IRB approval
- Investigator exceeding enrollment limits specified by Sponsor or IRB
- Treated subject did not meet inclusion/exclusion criteria.
- Subject did not attend follow-up visit (missed visit)
- Follow-up visit outside of the protocol-defined window
- Unauthorized use of an investigational product in the study by a physician who has not signed a Trial Agreement and/or whose training was not documented
- AE not reported by Investigator in the required regulatory timeframe

If a deviation involves a failure to obtain a subject's consent prior to use of an investigational device or is made to protect the life or physical well-being of a subject in an emergency, the deviation must be reported to the IRB as well as Medtronic within five (5) working days. Reporting of all other study deviations should comply with IRB policies and must be reported to Medtronic as soon as possible upon the site becoming aware of the deviation. Refer to Investigator Reports, Table 9 for deviation reporting requirements and timeframes for reporting to Medtronic.

All study deviations must be reported on an eCRF regardless of whether medically justifiable, an inadvertent occurrence, or taken to protect the subject in an emergency.

Medtronic is responsible for analyzing deviations, assessing their significance, and identifying any additional corrective and/or preventive actions (e.g., amend the CIP, conduct additional training, terminate the investigation). Repetitive or serious Investigator compliance issues may result in initiation of a corrective action plan with the Investigator and site, and in some cases, necessitate suspending enrollment until the problem is resolved or ultimately terminating the Investigator's participation in the study.

10 ADVERSE EVENTS AND DEVICE DEFICIENCIES

Timely, accurate, and complete reporting and analysis of safety information for clinical studies are crucial for the protection of subjects. Reporting and analysis of safety data are mandated by regulatory authorities worldwide. Medtronic has established procedures in conformity with worldwide regulatory requirements to ensure appropriate reporting of safety information. This study is conducted in accordance with these procedures and regulations.

10.1 Adverse Event and Device Deficiency Definitions

Adverse event and device deficiency definitions are provided in Table 6. Where the definition indicates "device", it refers to any Visualase System component used in the study.

Table 6: Adverse Event Definitions

General				
A L	General			
Adverse Event (AE)	Any untoward medical occurrence, unintended disease or injury, or untoward clinical signs (including abnormal laboratory findings) in subjects, users or other persons, whether or not related to the investigational medical device			
	NOTE 1: This definition includes events related to the investigational medical device or the comparator. NOTE 2: This definition includes events related to the procedures involved. NOTE 3: For users or other persons, this definition is restricted to events related to investigational medical devices. (ISO 14155:2011, 3.2)			
	NOTE: The specific adverse events collected for this study are described in Section 10.2.1			
Adverse Device Effect (ADE)	Adverse event related to the use of an investigational medical device			
	NOTE 1: This definition includes adverse events resulting from insufficient or inadequate instructions for use, deployment, implantation, installation, or operation, or any malfunction of the investigational medical device. NOTE 2: This definition includes any event resulting from an error use or from intentional misuse of the investigational medical device. (ISO 14155:2011, 3.1)			
Device Deficiency (DD)	Inadequacy of a medical device with respect to its identity, quality, durability, reliability, safety or performance.			
	NOTE: Device deficiencies include malfunctions, use errors and inadequate labeling (ISO 14155:2011, 3.15)			
	Relatedness			
Device-Related	An adverse event that is directly related to the use, presence and/or performance of the Visualase System.			
Procedure-Related	An adverse event that is not directly related to the Visualase System but is directly attributable to the surgical procedure in which Visualase was used. For the purpose of determining adverse event relatedness, the procedure begins at first scalp incision and ends at closure of all scalp incisions.			
Anesthesia-Related	An adverse event that is not directly related to the Visualase System, nor to the Visualase procedure, but is directly attributable to the anesthesia for the Visualase procedure.			
Epilepsy-Related	An adverse event related to the subject's epilepsy or AEDs.			

Seriousness			
Serious Adverse Event (SAE)	Adverse event that a) led to death, b) led to serious deterioration in the health of the subject, that either resulted in 1) a life-threatening illness or injury, or 2) a permanent impairment of a body structure or a body function, or 3) in-patient or prolonged hospitalization, or 4) medical or surgical intervention to prevent life-threatening illness or injury or permanent impairment to a body structure or a body function, c) led to fetal distress, fetal death or a congenital abnormality or birth defect NOTE 1: Planned hospitalization for a pre-existing condition, or a procedure required by the CIP, without serious deterioration in health, is not considered a serious adverse event. (ISO 14155:2011, 3.37)		
Serious Adverse Device Effect	Adverse device effect that has resulted in any of the consequences characteristic of a serious adverse event. (ISO 14155:2011, 3.36)		
Unanticipated Adverse Device Effect (UADE)	Any serious adverse effect on health or safety or any life-threatening problem or death caused by, or associated with, a device, if that effect, problem, or death, was not previously identified in nature, severity, or degree of incidence in the investigational plan or application (including a supplementary plan or application), or any other unanticipated serious problem associated with a device that relates to the rights, safety, or welfare of subjects. (21 CFR 812.3(s))		
	Duration		
Transient	Short-lived, not permanent. For the purpose of this study, adverse events lasting 30 days or fewer are considered transient.		
Prolonged	Continuing, persistent. For the purpose of this study, adverse events lasting more than 30 days but that do not meet the definition of permanent.		
Permanent	Long-lasting, for a year or longer. For the purpose of this study, adverse events not resolved at study exit will be considered permanent.		
Severity			
Mild	A type of adverse event that is usually transient and may require only minimal treatment or therapeutic intervention. The event does not generally interfere with usual activities of daily living. (CDISC)		
Moderate	A type of adverse event that is usually alleviated with additional specific therapeutic intervention. The event interferes with usual activities of daily living, causing discomfort but poses no significant or permanent risk of harm to the research participant. (CDISC)		

